| PPD | | 3/18/2019 1:21:25 PM |

| Document ID | Version | Approved Date in CET* | Pages |
|-------------|---------|------------------------|-------|
| PPD | 1.0 | Mar 18,2019 1:21:00 PM | 4 |

*CET: Central European Time

GlaxoSmithKline Consumer Healthcare
[name]
[name]
United States of America

March 18, 2019

RE: Protocol Administrative Changes #02 for Study 209723

RANDOMIZED CONTROLLED EXAMINER-BLIND PHASE II EXPLORATORY CLINICAL STUDY TO CHARACTERIZE THE EFFICACY PROFILE OF AN EXPERIMENTAL DUAL ACTIVE COMBINATION DENTIFRICE FOR THE RELIEF OF DENTIN HYPERSENSITIVITY, IN SUBJECTS WITH CLINICALLY DIAGNOSED DENTIN HYPERSENSITIVITY

Dear Investigator,

This letter is being sent to notify you of the following clarifications and administrative changes to the 209723 protocol; version 2.0, dated 16 Oct 2018.

Points of Clarification:

- **Section 6.7 Subject Compliance**, the following statement is added for clarification.

As this is an exploratory study, no specific thresholds for compliance/non-compliance have been defined. Compliance will be assessed at the Blind Data Review Meeting (Section 12.2.2 Exclusion of Data from Analysis), prior to database lock, to identify subjects with protocol deviations which would warrant exclusion of data from the mITT analysis population.
- **Section 10.7.1 Sponsor's Reporting Requirements to Regulatory Authorities and Ethics Committees**, the following statement is added for clarification.

SAEs and SUSARs will be reported in an expedited manner to Health Canada as per the NNHPD Clinical Trials for NHPs guidance document (<https://www.canada.ca/en/health-canada/services/drugs-health-products/natural-non-prescription/legislation-guidelines/guidance-documents/clinical-trials.html>).

- **Section 12.1 Sample Size Determination**, the following statement

Approximately 104 subjects will be randomized to study treatment (approximately 52 per treatment group)

is changed to

Approximately 104 subjects will be randomized to study treatment (approximately 52 per treatment group) to achieve approximately 50 evaluable subjects per treatment group, allowing for a dropout rate of approximately 4%.

for clarification.

Minor Administrative Changes:

- Protocol Administrative Change Letter #01 for Study 209723 referenced Section 9.9.2 in error, this is corrected to Section 9.2.2; stated NJ 07094 as ZIP code for the sponsor address in error, this is corrected to NJ 07059.
- **Section 1.1 Schedule of Activities, Table 1-1, Procedure/Assessment at Visit 6, Day 28 (± 2 days)**, the following statement is removed.

Provide Subject with New Diary

The diary provided at Visit 2 (Day 0, Baseline) will cover the entire 8-week treatment period; subjects will not be re-supplied with a diary at Visit 6.

- **Section 8.2.1 Baseline: Day 0 (Visit 2)**, the following statement is removed.

Clinical examiner completes an OHT examination. Record findings in the CRF.

OHT (oral hard tissue) examinations will be completed at Visit 1 (Screening) and Visit 7 (Day 56) only, as per Table 1.1 Schedule of Activities.

- **Section 9.1.4 Qualifying Tactile Sensitivity**, the following statement

The subject may respond "yes" if they feel pressure as the probe is applied to their tooth. The examiner will remind them they should only respond 'yes' if they feel PAIN or DISCOMFORT.

is corrected to

The subject may respond "yes" if they feel pressure as the probe is applied to their tooth. The examiner will remind them they should only respond 'yes' if they feel PAIN or DISCOMFORT.

**NO ADDITIONAL CHANGES HAVE BEEN MADE TO THE STUDY
DOCUMENTATION.**

Sincerely,

PPD

PPD

PPD

Clinical Research

18 Mar 2019

Date

cc: Trial Master File, IRB/EC

Document History

| Document | Version | Summary of Changes |
|-------------------|---------|--------------------|
| Original protocol | 2.0 | N/A |
| | | |
| | | |
| | | |

Amendments incorporate all revisions to date, including amendments made at the request of country health authorities, institutional review boards/ethics committees (IRBs/ECs), etc.

Principal Investigator Protocol Agreement Page

- I confirm agreement to conduct the study in compliance with the protocol and any amendments according to the current International Conference on Harmonisation Good Clinical Practice (ICH GCP) guidelines.
- I acknowledge that I am responsible for overall study conduct. I agree to personally conduct or supervise the described study.
- I agree to ensure that all associates, colleagues and employees assisting in the conduct of the study are informed about their obligations. Mechanisms are in place to ensure site staff receives all appropriate information throughout the study.
- I agree to conduct this study in full conformance with the laws and regulations of the country in which the research is conducted and the Declaration of Helsinki.

| | |
|------------------------------|--|
| Investigator Name: | |

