12.2.1 Definition of Analysis Populations

The Safety population will include all randomized subjects who receive at least one dose of study product. This population will be based on the product the subject received.

The modified Intent-To-Treat (mITT) population will include all randomized subjects who receive at least one dose of study product and have at least one post baseline efficacy measurement. This population will be based on the study product to which the subject was randomized. Any subject who receives a randomization number will be considered to have been randomized.

The Per-Protocol (PP) population will include all randomized subjects who do not have any protocol deviations that could confound the interpretation of analyses conducted on the mITT.

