12.2.2 Exclusion of Data from Analysis

Exclusion of any data from the analyses will be determined during a Blind Data Review Meeting prior to database lock. Any reasons for exclusion from an analysis population will be listed, if applicable. A PP analysis will be performed only if 10% or more of the subjects from the mITT population are excluded from the PP population.

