3.3 Timepoints and Visit Windows

The time points and visits for this study are defined in [Table 1-1](#) “Schedule of Activities”. Any deviation from the study schedule will be reviewed on case-by-case basis at the Blinded Data Review Meeting (BDRM) to determine whether the data should be excluded from the Per-Protocol (PP) population.

4 Data Analysis

Data analysis will be performed by Syneos Health. Statistical analysis software SAS (Studio) version 9.4 or higher will be used.

Prior to database closure a BDRM will be conducted at which various aspects of the trial will be discussed and necessary actions, including exclusions from the Safety, modified Intent to Treat (mITT) and PP populations.

Unless otherwise described below, listings will be produced for all randomized subjects.

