4.1.2 Protocol Deviations

Protocol deviations will be tracked by the study team throughout the conduct of the study. Data will be reviewed prior to unblinding and closure of the database to ensure all important deviations are captured and categorized. Subjects with important protocol deviations liable to influence the efficacy outcomes will be excluded from the PP population. Subjects may also be identified as having important protocol deviations not leading to exclusion from the PP population.

Important deviations from protocol procedures may include, but will not be necessarily be limited to the following:

- Consent procedures
- Inclusion/exclusion criteria
- Study procedures

The specific details of important protocol deviations will be listed in Protocol Deviation Management Plan (PDMP) and assessment process will be specified in the Blind Data Review Plan. Subjects with important protocol deviations will be identified at the BDRM.

The number and percentage of subjects with at least one important protocol deviation, with at least one important protocol deviation not leading to exclusion from PP population (with reasons for deviations) and with important protocol deviations leading to exclusion from the PP population (with reasons for deviations) will be presented in [Table 14.1.2](#) by study product and listed in [Listing 16.2.2.1](#).

Protocol deviations collected on the protocol deviation page of the electronic Case Report Form(eCRF) will be listed in [Listing 16.2.2.2](#). The listing will present date of deviation, type of deviation and deviation description.

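### The statement added to Section 6.7 lets compliance deviations remove data from the mITT population, although the mITT definition has no compliance condition and the SAP's specific deviation rules lead only to PP exclusion

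*Protocol*

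**What the plan says.** **Protocol, Administrative Changes #02 letter (18 March 2019), addition to Section 6.7.** The letter states that "no specific thresholds for compliance/non-compliance have been defined" and that compliance will be assessed at the blinded review before database lock "to identify subjects with protocol deviations which would warrant exclusion of data from the mITT analysis population". It closes with "NO ADDITIONAL CHANGES HAVE BEEN MADE TO THE STUDY" documentation, so it leaves the population definitions as they were.

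**Protocol 12.2.1.** The text on mITT reads: "population will include all randomized subjects who receive at least one dose of study product and have at least one post baseline efficacy measurement". SAP 4.1.3 repeats this definition. Neither version has a compliance or deviation condition. PP is the only population that either document defines by the absence of deviations.

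**Protocol 12.2.2.** Data exclusions are decided at the Blind Data Review Meeting, and a PP analysis is run "only if 10% or more of the subjects from the mITT population are excluded from the PP population". SAP 4.1.3 sets the trigger at more than 10%.

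**SAP, specific deviation rules.** Section 4.1.2: "Subjects with important protocol deviations liable to influence the efficacy outcomes will be excluded from the PP population". Section 3.3 sends visit-schedule deviations to the review meeting "to determine whether the data should be excluded from the Per-Protocol (PP) population".

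**SAP Section 4, opening text.** The review meeting will discuss "necessary actions, including exclusions from the Safety, modified Intent to Treat (mITT) and PP populations". No criteria are given there.

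**SAP 4.3.1** summarizes missed and additional brushings within mITT.

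**The concern.** The Section 6.7 statement and the mITT definition cannot both be applied as written. A randomized subject who used the product, has post-baseline efficacy data and brushed irregularly belongs to mITT by definition, yet is a candidate for exclusion from it under Section 6.7. Protocol 8.3 treats every missed or additional application as a protocol deviation, so the pool of candidates is open-ended, and no threshold limits it.

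Two things are at stake.

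- **The Day 56 comparisons.** mITT is the efficacy population for the Schiff and tactile ANCOVAs. Compliance is a post-randomization variable. If it differs by arm and relates to outcome, excluding on it breaks the randomized comparison. Protocol Section 3 counts a significant Day 56 Schiff difference in favour of Test as success, so this comparison carries weight although it is a secondary endpoint. Because no data are imputed (Protocol 12.2.9, SAP 4.4.3), removing the subject or only the Day 56 data has the same effect on the Day 56 model.
- **The supportive analysis.** Subjects taken out of mITT altogether no longer count as mITT subjects excluded from PP. The analysis meant to show the effect of deviations may then not be triggered.

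**Working it through.** **1. The plan's own figure.** The letter and SAP 1.4 give 52 randomized per group for about 50 evaluable, at about 4% dropout. 50/0.96 = 52.1 and 52 × 0.96 = 49.9, so 104 in total reproduces within rounding. The conflict does not depend on this figure; it only supplies the denominator below.

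**2. The texts side by side.**

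| Source | What a deviation does |
|---|---|
| Letter, Section 6.7 addition | Compliance deviations may exclude data from mITT |
| Protocol 12.2.1, SAP 4.1.3 (mITT) | No effect on membership |
| Protocol 12.2.1, SAP 4.1.3 (PP) | Confounding deviations exclude from PP |
| SAP 4.1.2 | Important deviations liable to affect efficacy exclude from PP |
| SAP 3.3 | Schedule deviations may exclude from PP |
| SAP 4, opening | Meeting may act on Safety, mITT and PP; no criteria given |

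The Section 6.7 addition is the only text that names mITT as the target of a particular kind of deviation.

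**3. PP trigger.** This applies only if whole subjects leave mITT. Let n be the number of subjects with excluding deviations among 104, and k the number of those taken out of mITT instead of PP. The share that decides whether PP is run is (n − k)/(104 − k). With 104 in mITT, at least 11 are needed under either wording of the trigger, because 10/104 = 9.6%.

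| n | k = 0 | Smallest k that stops the PP analysis |
|---|---|---|
| 11 | 11/104 = 10.6% | k = 1: 10/103 = 9.7% |
| 12 | 12/104 = 11.5% | k = 2: 10/102 = 9.8% |
| 13 | 13/104 = 12.5% | k = 3: 10/101 = 9.9% |
| 15 | 15/104 = 14.4% | k = 6: 9/98 = 9.2% |

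Moving all 11 in the first row gives 0/93. With 100 in mITT, 6 non-compliers and 6 other deviators, routing all 12 to PP gives 12%, and PP is run. Taking the 6 non-compliers out of mITT gives 6/94 = 6.4%, and it is not.

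**4. Illustration of bias.** The documents give no compliance or outcome data, so these inputs are assumptions: no true treatment effect; 52 per arm; a and b subjects excluded from the two arms; excluded subjects worse than retained ones by δ = 0.5 to 1 SD, the same in both arms.

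- Bias in SD units = (a/52 − b/52) × δ
- SE = √[1/(52 − a) + 1/(52 − b)]
- Two-sided rejection = P(Z > 1.96 − bias/SE) + P(Z < −1.96 − bias/SE)

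| a v b | SE | Bias (δ = 0.5; 1) | Rejection (δ = 0.5; 1) |
|---|---|---|---|
| 5 v 5 | √(1/47 + 1/47) = 0.206 | 0; 0 | 5.0%; 5.0% |
| 5 v 2 | √(1/47 + 1/50) = 0.203 | 0.029; 0.058 | 5.2%; 5.9% |
| 5 v 0 | √(1/47 + 1/52) = 0.201 | 0.048; 0.096 | 5.7%; 7.7% |

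The last row is the worst split of five exclusions.

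**The case against.** The strongest reply is that the later SAP (27 September 2019) already settles the matter. Protocol 8.3 makes missed brushings deviations, SAP 4.1.2 has an open-ended list that includes study procedures, and such deviations therefore already lead to PP exclusion. The opening of SAP Section 4 also mentions Safety, which has no compliance condition either, so it may mean only that the meeting confirms each population by its own definition. On this view, mITT in the letter is a slip, or a compressed reference to Protocol 12.2.2, where mITT subjects are excluded from PP.

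Much of this is fair. The SAP does lean clearly towards PP, and a slip is plausible. But the SAP does not withdraw the Section 6.7 statement, although it carries over the same letter's 4% dropout wording, and SAP Section 5 declares no changes from the protocol's analysis. A review meeting could cite text for either route. If it is a slip, that is a reason to correct it.

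The consequences are also conditional. The PP flip needs whole-subject removal and at least 11 affected of 104. The bias needs adherence to differ by arm and relate to outcome, and the 0.5 to 1 SD gap is assumed. These limits stand: they restrict the size of the problem but do not remove the contradiction.

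A further point is that the first sentence of Protocol 12.2.2 names no population and would still allow data exclusions after the Section 6.7 wording is corrected. That is why the SAP sentence in the fix has to cover all deviations, not compliance alone.

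The Protocol Deviation Management Plan and Blind Data Review Plan cited in SAP 4.1.2 are not available, so nothing is claimed about their criteria.

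**Conclusion.** The concern holds and should be fixed. The Section 6.7 addition is current text that, read literally, permits compliance-based exclusions from mITT with no threshold. It contradicts the mITT definition in both documents and departs from the SAP's specific deviation rules. Confidence in the textual conflict is high.

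The size of any bias cannot be derived from the documents. Under the stated assumptions it ranges from none, with balanced exclusions and an equal gap in both arms, to a rejection rate of 7.7% when all five exclusions fall in one arm and δ is 1 SD. Blinded review limits it. The loss of the PP analysis is plain arithmetic, but it arises only if whole subjects leave mITT and the number affected is near or above the trigger.

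The primary endpoints are descriptive and the study is exploratory. The exposure therefore lies in the secondary Day 56 comparisons, chiefly the Schiff success criterion.

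**What to change.** 1. In the statement added to Protocol Section 6.7, name the PP analysis population in place of mITT.
2. In SAP Section 4, state that the review meeting confirms Safety and mITT membership solely by the definitions in 4.1.3, and that compliance and all other protocol deviations lead to exclusion from PP only.

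The change is one population name and one sentence; no endpoint, model or sample size is affected. The downside is that poor compliers stay in mITT, so its estimate of the treatment difference may be slightly diluted.

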1 PROTOCOL SUMMARY

Background and Rationale

GlaxoSmithKline Consumer Healthcare (GSK CH) has developed an anhydrous 5% potassium nitrate (KNO₃) and 0.454% stannous fluoride (SnF₂) combination dentifrice for the relief of dentin hypersensitivity (DH). It is hypothesized that the combination of two anti-sensitivity active ingredients with complementary modes of action (KNO₃: nerve desensitization; SnF₂: dentin tubule occlusion) will deliver superior anti-sensitivity efficacy, compared to either active alone. Published clinical studies report DH efficacy for KNO₃/SnF₂ combination dentifrices and indicate greater clinical benefit for dual active formulations, compared to KNO₃ only formulations, with 4-8 weeks treatment. They do not provide any information regarding performance versus SnF₂ only formulations (no SnF₂ only dentifrices were evaluated). This exploratory study will characterize the efficacy profile of an experimental 5% KNO₃ and 0.454% SnF₂ combination dentifrice, compared to a 0.454% SnF₂ single active desensitizing dentifrice, across an 8-week treatment period.

Objectives and Endpoints

| Objectives | Endpoints |
|--|---|
| Primary | |
| To characterize the efficacy profiles of an experimental 5% w/w KNO ₃ and 0.454% w/w SnF ₂ combination dentifrice and a 0.454% w/w SnF ₂ only dentifrice in reducing DH, with twice daily use for 8 weeks. | At Baseline, Days 3, 7, 14, 28, 56; Schiff sensitivity score Tactile threshold (grams [g]) Number of sensitive teeth (Schiff sensitivity score ≥ 1) |
| Secondary | |
| To investigate the clinical efficacy of an experimental 5% w/w KNO ₃ and 0.454% w/w SnF ₂ combination dentifrice in reducing DH to an evaporative air stimulus (Schiff sensitivity score), compared to a 0.454% w/w SnF ₂ only dentifrice, after 8 weeks twice daily use. | Change from Baseline in Schiff sensitivity score at Day 56 |
| To investigate the clinical efficacy of an experimental 5% w/w KNO ₃ and 0.454% w/w SnF ₂ combination dentifrice in reducing DH to a tactile stimulus (tactile threshold), compared to a 0.454% w/w SnF ₂ only dentifrice, after 8 weeks twice daily use. | Change from Baseline in tactile threshold (g) at Day 56 |
| Safety | |
| To assess the safety and tolerability of an experimental 5% w/w KNO ₃ and 0.454% w/w SnF ₂ combination dentifrice with twice daily use for 8 weeks. | Treatment emergent adverse events |
| Other | |
| To investigate the clinical efficacy of an experimental 5% w/w KNO ₃ and 0.454% w/w SnF ₂ combination | At Days 3, 7, 14 & 28; Change from Baseline in Schiff |

| | |
|---|--|
| dentifrice in reducing DH to evaporative air (Schiff sensitivity score) and tactile (tactile threshold) stimuli, compared to a 0.454% w/w SnF ₂ only dentifrice, after 3, 7, 14 & 28 days twice daily use. | sensitivity score Change from Baseline in tactile threshold (g) |
| To monitor Oral Health Related Quality of Life (OHRQoL) as measured by the Dentine Hypersensitivity Experience Questionnaire (DHEQ) after 4 and 8 weeks treatment with an experimental 5% w/w KNO ₃ and 0.454% w/w SnF ₂ combination dentifrice and a 0.454% w/w SnF ₂ only dentifrice | At Days 28 & Day 56; Change from Baseline in 
 - responses to Questions 7-9, DHEQ Section 1 - Total Score, Questions 1-15, DHEQ Section 2 - Restrictions, Adaptation, Social Impact, Emotional Impact & Identity Domains |

Study Design

This will be a single center, 8-week, randomized, controlled, examiner-blind, two treatment arm, parallel design, stratified (by maximum Baseline Schiff sensitivity score of the two selected test teeth), Phase II, exploratory study to evaluate the DH efficacy of an experimental 5% KNO₃ and 0.454% SnF₂ combination dentifrice (Test), compared to a marketed 0.454% SnF₂ desensitizing dentifrice (Control). Study dentifrices will be applied twice daily, by toothbrushing, over the 8-week treatment period.

DH to tactile and evaporative air stimuli will be assessed at Screening (Visit 1) and Baseline (Visit 2), and after 3, 7, 14, 28 and 56 days treatment (Visits 3-7). Eligible subjects will complete an acclimatization phase (2-4 weeks) between the Screening and Baseline visits and will be randomized to study dentifrice following Baseline assessments. The safety and oral tolerability of the study products will be monitored over the treatment period by review of reported adverse events (AEs).

Study Products

| | Acclimatization Dentifrice | Test Dentifrice | Control Dentifrice |
|-----------------------|--|---|---|
| Treatment Description | Dentifrice containing 1000 parts per million (ppm) fluoride as sodium monofluorophosphate (SMFP) | Dentifrice containing 5% w/w KNO ₃ and 0.454% w/w SnF ₂ (1100 ppm fluoride) | Dentifrice containing 0.454% SnF ₂ (1100 ppm fluoride) |
| Product Name | Colgate Cavity Protection (Canadian market) | Experimental dentifrice | Sensodyne Rapid Relief Regular (registered as a Non-prescription Natural Health Product [NNHP] in Canada) |

Type and Planned Number of Subjects

The study will be conducted in male and female subjects in good general health, aged 18-65 years, with pre-existing self-reported tooth sensitivity, and at least two sensitive teeth (confirmed clinically) that meet all study criteria at both the Screening (Visit 1) and Baseline (Visit 2, pre-treatment) visits. Sufficient subjects will be screened (approximately 150 subjects) to enter approximately 125 subjects into the acclimatization phase to ensure approximately 104 subjects are randomized to study treatment (approximately 52 subjects per treatment arm).

Statistical Analyses

A modified Intent-To-Treat (mITT) population will be used for efficacy analyses.

The primary efficacy variables are Schiff sensitivity score and tactile threshold (g), both calculated as the average score of the two test teeth, and the number of sensitive teeth (Schiff sensitivity score ≥ 1) at Day 0 (Baseline), Day 3, Day 7, Day 14, Day 28 and Day 56. Summary statistics (mean, median, standard error (SE), standard deviation (SD), minimum, maximum) will be presented for each outcome variable at each assessment time point. Raw means (\pm SE) of Schiff sensitivity score, tactile threshold (g) and number of sensitive teeth at each timepoint will be plotted by treatment group.

The secondary efficacy variables are change from Baseline in Schiff sensitivity score and the change from Baseline in tactile threshold (g), at Day 56. Change from Baseline in Schiff sensitivity score will be analysed at Day 56 using an analysis of covariance (ANCOVA) model which will include treatment as a factor and Baseline Schiff sensitivity score as a covariate. Change from Baseline in tactile threshold (g) will be analysed at Day 56 using an ANCOVA model with treatment and Baseline Schiff stratification included as factors and Baseline tactile threshold included as a covariate. Adjusted mean change from Baseline, along with 95% confidence intervals (CIs) will be reported by treatment group. P-values testing for non-zero change from baseline will be presented for both treatment groups. The mean difference between treatment groups, 95% CIs and p-values will be provided. Significance testing will be conducted at the two-sided 5% significance level with no adjustments for multiple testing.

